8.1.1.1 FRI parameters

Image acquisition

In this study, the FRI parameters will be obtained through first the acquisition of low dose, high-resolution computed tomography (CT) thorax scans of participants in the study using a low radiation scanning protocol installed on a study-allocated CT scanner before study initiation at the study center.

All participants in the study will undergo two high-resolution scans, one each at Total Lung Capacity (TLC) and Functional Residual Capacity (FRC) with gating, at both Visits 1 and 4 as specified in the SoA (Table 1). All CT scans will be conducted with respiratory gating using equipment (CE-marked) provided by the central vendor. All CT scan procedures should also be conducted before spirometry testing (see Section 8.1.2 for further details).

Participants should withhold their usual maintenance and rescue therapies **before Visit 1 and Visit 4** where CT procedures will be scheduled as below:

- Short-acting muscarinic antagonists (SAMAs) or CCI /SAMA combinations should be withheld at least 12 hours prior to Visit 1 and Visit 4 at the site.
- Twice daily LABA-containing therapies should be withheld for at least 12 hours prior to Visit 1 and Visit 4 at the site.
- Once daily LABA-containing therapies should be withheld for at least 24 hours prior to Visit 1 and Visit 4 at the site.
- Once daily LAMA-containing therapies should be withheld for at least 24 hours prior to Visit 1 and Visit 4 at the site.
- Twice daily LAMA-containing therapies should be withheld for at least 12 hours prior to Visit 1 and Visit 4 at the site.

- LTRA should be restricted for at least 24 hours prior to Visit 1 and Visit 4 at the site.
- Twice daily theophyllines should be withheld for at least 12 hours prior to Visit 1 and Visit 4 at the site.
- Once daily theophyllines for at least 24 hours prior to Visit 1 and Visit 4 at the site.

Image processing

All high-resolution CT images should be de-identified before upload to the central vendor where they will be imported into Mimics, a commercial, Food and Drug Administration approved, medical image processing software package (Materialise, Leuven, Belgium, Food and Drug Administration, K073468; CE certificate, BE 05/1191 CE01). Trained FRI analysts will implement validated protocols and algorithms to convert the high-resolution CT images into patient specific, segmented, three-dimensional (3D) computer models of the lung lobes, the airway lumen and wall, and the vascular tree. These models will then be used for performing measurements of the following structural and functional FRI parameters and used for further evaluations of functional FRI parameters that utilize computational fluid dynamics (CFD).

The following are the relevant structural and functional FRI parameters:

- 1. Untrimmed total mucus volume at TLC (Primary)
- 2. Untrimmed total mucus plugs score at TLC (Secondary)
- 3. Untrimmed total air trapping at FRC (Secondary)
- 4. Trimmed distal airway wall volume (iVaww) at TLC (Secondary)
- 5. Trimmed distal specific airway volume (siVaw) at TLC (Secondary)
- 6. Trimmed distal specific airway volume (siVaw) at FRC (Secondary)
- 7. Untrimmed total lung volume (iVlung) at TLC (Secondary)
- 8. Untrimmed total lung volume (iVlung) at FRC (Secondary)
- 9. CCI

The computational fluid dynamics (CFD) approach will also be used to model exposure to inhaled particles. Specifically, aerosol deposition using CFD simulates the particle flow and particle behavior of within the reconstructed lungs of participants as a function of the specific inhalation profile, geometry of the airways and the drug particle size. In this study, aerosol deposition will be simulated based on inhalation of a generic ^{CCI}

CCI inhaler using selected inhalation flow profiles. Specific particle mass median aerodynamic diameter (MMAD +/- geometric standard deviation) of the relevant drug will be taken from published literature or data on file and 3D computer-aided design (CAD) file of the inhaler device will be obtained to conduct the aerosol deposition simulation.

Deposition in the intrathoracic and peripheral airways will be measured using drug deposition ratio before and after benralizumab treatment using lung models from high-resolution CT scans at week 0 (baseline) and week 13 (\pm 5 days). Central airway will be defined as the trachea and all airways with diameter > 1-2 mm and reaching out to 7–10th generation of dichotomous branching, while the peripheral airways will be defined as airways with a diameter < 1-2 mm and > 10 generations of branching. As detailed in the above list of relevant structural and functional FRI parameters, FRI analyses on CT scans at baseline (Visit 1) and following benralizumab treatment (at Visit 4) will be conducted on untrimmed or trimmed airways. Untrimmed analyses will include all airway branches visible at each visit, while the trimmed analysis will only include airway branches visible across both visits 1 and 4. All FRI parameters will be assessed in the different zones of the respiratory system - right upper lobe (RUL), right middle lobe (RML), right lower lobe (RLL), left upper lobe (LUL) and left lower lobe (LLL), as well as into central and distal regions, the latter two regions only for FRI parameters related to the airways (siVaw, and iVaww). Specifically, all FRI parameters related to the airways (siVaw and iVaww) will be assessed from generations 1 to 10 and reported by different zones of the respiratory system and by central and distal regions. Additionally, airway wall volume (iVaww) will be at generations 3 and 4, based on assessments planned for similar ongoing studies.

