3 OBJECTIVES AND OUTCOME MEASURES

Table 2 Objectives and Outcome Measures

See footnote for abbreviations mentioned on the table below.

Obj	jectives	Outcome measures ^a							
Prir	nary								
dyn ben airv	describe the change from baseline in airway amics after 13 weeks following treatment with ralizumab, using total mucus volume (specific way volume) measurements from untrimmed ways.	Unadjusted mean within subject difference in total mucus volume measured at TLC, calculated as the mean change from baseline (week 0) at week 13 (\pm 5 days).							
Sec	ondary								
1.	To describe the change from baseline in airway dynamics at week 13 following treatment with benralizumab, as measured by secondary FRI endpoints ^b , irrespective of patient characteristics.	Unadjusted mean within subject difference in secondary FRI endpoints (total mucus plugs score at TLC; total air trapping at FRC; trimmed distal iVaww at TLC; trimmed distal siVaw at TLC and FRC; total iVlung at TLC and FRC), comparing baseline (week 0) to week 13 (± 5 days).							
2.	To describe the relationship between airway dynamics and conventional lung function measurements, cross-sectionally (at week 0) and irrespective of patient characteristics.	Correlation between imaging endpoints (primary and secondary FRI endpoints ^b) and pre-bronchodilator forced expiratory volume in 1 second (pre-BD FEV ₁) at week 0. Correlation between imaging endpoints (primary and secondary FRI endpoints ^b) and pre-bronchodilator forced vital capacity (pre-BD FVC) at week 0. Scatter plots of primary and secondary FRI endpoints ^b and mucus plugs score versus conventional lung function measures (pre-BD FEV ₁ and pre-BD FVC) at week 0. Estimated increases in primary and secondary FRI endpoints ^b and mucus plugs score for every one percent increase in pre-BD FEV ₁ and pre-BD FVC at week 0.							

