3.	To describe the relationship between changes from baseline (week 0) in airway dynamics and conventional lung function measurements at week 13, after accounting for baseline measurements of conventional lung function.	Correlation between the change from week 0 in imaging endpoints (primary and secondary FRI endpoints ^b) at week 13 and the change from week 0 in pre-BD FEV ₁ at week 13 (\pm 5 days), overall and within subgroups conditional on the baseline value of pre-BD FEV ₁ . Correlation between the change from week 0 in imaging endpoints (primary and secondary FRI endpoints ^b) at week 13 and the change from week 0 in pre-BD FVC at week 13 (\pm 5 days), overall and within subgroups conditional on the baseline value of pre-BD FVC at week 13 (\pm 5 days), overall and within subgroups conditional on the baseline value of pre-BD FVC.							

	Scatter plots of changes from week 0 in primary and secondary FRI endpoints ^b and mucus plugs score at week 13 vs. changes from week 0 in conventional lung function measures (pre-BD FEV ₁ and pre-BD FVC) at week 13. Estimated change over time (week 13 vs. week 0) in primary and secondary FRI endpoints ^{ab} , with and without adjustment for conventional lung function measures (pre-BD FEV ₁ and pre-BD FVC).
Safety	
To monitor the safety and tolerability of benralizumab.	 Safety and tolerability will be evaluated in terms of AEs, Vital signs, and Clinical laboratory. Assessments related to AEs include: Occurrence/Frequency Relationship to IP or study procedure as
	assessed by investigator
	– Intensity
	- Seriousness
	– Death
	 AEs leading to discontinuation of IP
	 Other significant AEs
	 Time to onset
	Vital signs parameters include systolic and diastolic blood pressure, and heart rate.
/ CCI	
CCI	

- a. FRI endpoints are untrimmed unless otherwise specified (Section 8.1.1.1).
- b. The primary FRI endpoint is total mucus volume at TLC; secondary FRI endpoints for evaluation under secondary objectives include total mucus plugs score at TLC, total air trapping at FRC; trimmed distal iVaww at TLC; trimmed distal siVaw at TLC and FRC; total iVlung at TLC and FRC; and total mucus plugs score at TLC.

CCI	; AE =
adverse event; CCI	; $FEV_1 = Forced$ expiratory volume in 1 second; $FRC = Functional$
residual capacity; FRI = Funct	onal Respiratory Imaging; FVC = Forced vital capacity; IP =
investigational product; iVaw	= Airway wall volume, iVlung = Lung volume, CCl
CCI ;CCI	; (CC)

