9.4.4 Other Analyses

Further analyses will be conducted for the secondary objectives related to crosssectional associations between imaging (FRI) endpoints and conventional lung function measurements (FEV₁ and FVC) at week 0. These analyses will use measurements from the study population that includes both participants who completed the study per protocol definition, and those who completed baseline measurements at Visit 1 and had at least one dose of IP irrespectively of whether they discontinued for reasons described in Section 7.1.

CCI

The evaluable population (Table 4) will be analyzed for the same outcome measures conducted for the primary analysis population (Table 4).

Additional analyses will be conducted for all outcome measures for both the primary analysis population and the evaluable population for the following subgroups:

- Mucus plugging status: Participants with or without mucus plugs identified at the CT scans (Section 8.1.1.2) at Visit 1 (week 0)
- OCS dependency status: OCS-dependent and Non-OCS-dependent participants as defined by the inclusion criteria #4 (Section 5.1)

Results from subgroup analyses above will be compared with corresponding results from the evaluable population.

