3.2.2.8 Subgroup Analyses

Subgroup analyses will be carried out as described in Section 3.2.1.8.

3.2.3 Secondary Endpoint 2 – Correlation Between Airway Dynamics and Lung Functions Measurements at Week 0

3.2.3.1	Definition

Table 6Definition of Secondary Endpoint 2

Population:	Baseline endpoints analysis set	
Endpoint:	 Baseline (Week 0) relationship between: pre-BD FEV₁ and each FRI parameter (primary and secondary) 	
	• pre-BD FVC and each FRI parameter (primary and secondary)	
Treatment:	Benralizumab 30 mg, 3 doses, once every 4 weeks (at baseline [V1], Week 4 [V2] and Week 8 [V3])	
Intercurrent events:	Participant withdrawal, IPD, use of prohibited medicines/substances, asthma exacerbation	
Population-level	Spearman's rank correlation coefficients	
summary:	Pearson correlation	
	Graphical summary (scatterplots)	
	Regression coefficients with 95% CI	

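### After the SAP Addendum, one parameter in the Week 0 correlations (trimmed distal iVaww at TLC) still cannot be computed without the Visit 4 scan

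*Protocol*

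**What the plan says.** Protocol 8.1.1.1 defines two kinds of airway measurement. For one, "Untrimmed analyses will include all airway branches visible at each visit"; for the other, "the trimmed analysis will only include airway branches visible across both visits 1 and 4". The Schedule of Activities (Protocol 1.3) places CT at Visits 1 and 4 and shows none at the early discontinuation visit.

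Secondary objective 2 in Protocol section 3 is "To describe the relationship between airway dynamics and conventional lung function measurements, cross-sectionally (at week 0) and irrespective of patient characteristics". The FRI endpoints it uses include "trimmed distal iVaww at TLC; trimmed distal siVaw at TLC and FRC". SAP Table 6 (section 3.2.3.1) crosses both FEV1 and FVC with all of them; its FVC entry reads, in part, "pre-BD FVC and each FRI parameter (primary and secondary".

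Table 6 names one population, the Baseline endpoints analysis set. The SAP amendment history records that the other sets were removed for this endpoint. Protocol 9.4.4 describes that population as including "those who completed baseline measurements at Visit 1 and had at least one dose of IP irrespectively of whether they discontinued". Protocol 7.1 likewise says that baseline measurements are still evaluated after permanent discontinuation, provided Visit 1 was completed and a dose was given. SAP 3.2.3.3 excludes only participants whose Week 0 measurements are missing.

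Three parts of the SAP Addendum bear on this:
- Section 1.4 replaces trimmed distal siVaw at TLC and FRC with untrimmed distal iVaw at TLC and FRC. It does not change trimmed distal iVaww at TLC.
- Section 2.14 removes participants with incomplete FRI parameters who lack a baseline or Week 13 assessment from the analysis of those parameters, while keeping them in the population.
- Section 1.1 lets a participant be evaluable with baseline and post-treatment data from any one of PROs, CT or spirometry.

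**The concern.** A cross-sectional Week 0 analysis should need only Week 0 data. A trimmed parameter needs both scans by definition, so two things follow when it enters objective 2.

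First, the named analysis set cannot be used in full for that parameter. A participant who had the Visit 1 scan and a dose, then stopped before Visit 4, has no trimmed Week 0 value, although the set was chosen to keep such people.

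Second, for a participant with both scans, the branches that count at baseline are selected by what is visible after treatment. The correlation and slope with baseline FEV1 or FVC then use an imaging value that depends partly on the post-treatment scan.

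At stake is whether the iVaww result in a descriptive secondary objective describes the population and the time point it claims to. The primary endpoint and all untrimmed parameters are untouched. Trimming remains coherent for change from baseline, where both scans are needed anyway.

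**Working it through.** **Plan's own figure.** The protocol gives 29 participants for the primary endpoint. The calculation in Protocol 9.2 is not in the public text, so 29 cannot be reproduced. Nothing below depends on it.

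**1. How many results are affected.** Protocol 8.1.1.1 labels eight FRI parameters as primary or secondary. Each is paired with FEV1 and FVC: 8 × 2 = 16 correlations.
- Protocol and SAP before the Addendum: iVaww at TLC, siVaw at TLC and siVaw at FRC are trimmed, so 3 of 8 parameters and 3 × 2 = 6 of 16 correlations.
- After Addendum 1.4: only iVaww at TLC is trimmed, so 1 of 8 parameters and 1 × 2 = 2 of 16 correlations.

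**2. Participants without a usable Visit 4 scan.** Let B1 be the distal branches visible at Visit 1 and B4 those visible at Visit 4. The trimmed Week 0 value is measured on the Visit 1 scan over the branches in both B1 and B4. Without a Visit 4 scan, B4 is unknown and the value is undefined. The untrimmed Week 0 value uses B1 alone and is defined.

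**3. Participants with both scans.** Taking wall volume as additive over branches:

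untrimmed Week 0 value − trimmed Week 0 value = Visit 1 wall volume of branches in B1 but not in B4.

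Only branches seen at Visit 1 and lost by Visit 4 change the baseline value. Branches that appear for the first time at Visit 4 were never in B1, so trimming them leaves Week 0 unchanged. The documents give no count or volume of lost branches, so the difference cannot be sized.

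**4. How many participants drop out of the parameter.** The synopsis plans 38 enrolled and 34 evaluable: 38 − 34 = 4, and 4/38 = 10.5%. This is a guide only, for two reasons.
- Enrolled means consented, so some of the 4 may be screen failures who were never dosed. That lowers the figure.
- Under Addendum 1.1 a participant can be evaluable without a Visit 4 CT, so some of the 34 may also lack one. That raises it.

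**5. Effect on precision.** The 95% interval for a Pearson correlation is tanh(atanh(r) ± 1.96/√(n − 3)). The half-width on the z scale is 1.96/√35 = 0.331 at n = 38 and 1.96/√31 = 0.352 at n = 34. The values of r are assumed for illustration.

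| Assumed r | n = 38 | n = 34 |
|---|---|---|
| 0.3 | −0.022 to 0.565 | −0.042 to 0.579 |
| 0.5 | 0.215 to 0.707 | 0.195 to 0.717 |

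A loss of 4 participants costs little precision. The point is one of definition, not power.

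**The case against.** The strongest reply is that the Addendum has already dealt with most of this. Much of it stands.

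- A reader of the protocol and main SAP might infer that three parameters are affected and that the eight baseline correlations cannot be compared with one another. Addendum 1.4 removes two of the three, so seven of eight are untrimmed in the operative plan. Its stated reason is the mode of action of biologics, but the effect is the same.
- A reader might infer that the analysis set shrinks silently. It does not: Addendum 2.14 writes down a per-parameter exclusion. That settles who is dropped. It does not make the Week 0 value independent of Visit 4.
- A reader might infer that airways opening on treatment distort the baseline value, or that the trimmed value says nothing about Week 0. Step 3 shows that opened airways have no effect at baseline. Opening is also the change Addendum 1.4 expects. The value is still measured on the Visit 1 scan, over a restricted set of branches, and may lie close to the untrimmed one.
- The columns of SAP Table 2 that specify the transferred variable are redacted, so a Visit 1-only iVaww may already be supplied. The visible text calls the parameter trimmed and gives no alternative, but this needs checking.
- One iVaww definition across objectives 1, 2 and 3 keeps the baseline correlation and the change analysis on the same quantity. This is a real advantage, but it does not outweigh a Week 0 value that some members of the named analysis set cannot have.

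**Conclusion.** The point holds for one parameter. After Addendum 1.4, trimmed distal iVaww at TLC in secondary objective 2 (2 of 16 correlations) has no Week 0 value for a Baseline endpoints set participant without a usable Visit 4 scan. For everyone else, its Week 0 value depends on which branches are still visible after treatment. The planned loss is about 4 of 38 or fewer, without being a firm bound, and the cost in precision at that loss is small. The shift in values for participants with both scans is unknown and may be small; the documents do not support calling it a material bias.

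This rests on the trimming definition in Protocol 8.1.1.1 applying to the Week 0 value as transferred, and on no Visit 1-only iVaww being hidden in the redacted columns of SAP Table 2. The change is worth making because it is cheap and lets the stated analysis set answer the stated Week 0 question.

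**What to change.** - For secondary objective 2, use untrimmed distal iVaww at TLC from the Visit 1 scan alone, for everyone in the Baseline endpoints set. Say so in SAP Table 2, Table 6 and section 3.2.3.4, or in the Addendum.
- Do the same in any other Week 0 cross-sectional analysis that takes all FRI parameters, such as SAP 3.2.5.
- Keep trimmed iVaww for the change-from-baseline analyses (objectives 1 and 3).
- State in Addendum 2.14 that a Week 0 analysis requires only the Week 0 value, so that a missing Week 13 assessment does not exclude anyone from it.
- Report N for each parameter.
- Check the data-selection columns of SAP Table 2 to confirm which iVaww variable is transferred.

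The cost is SAP wording and one extra variable from Visit 1 airway models that the imaging vendor already builds. No new scan is needed. The one drawback is that objectives 1 and 2 would then report different versions of iVaww, which a table footnote should state.

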8.1.1.2 Mucus Plugging

As detailed in the previous section, untrimmed total mucus volume at TLC and untrimmed mucus plugs score at TLC are FRI parameters of interest in the study.

Mucus plugging will be assessed visually through diligent segmentation of the airways. Airways will be segmented from central airways to distal airways by means of a deep learning Convolutional Neural Network (CNN) model to the extent which the resolution of the scanner allows. After segmentation of the airways, a mucus plug will be identified as such if the plug prematurely blocks or ends the airway segmentation and presents with an open airway after the plug (full occlusion). The above approach to mucus plug assessment allows for multiple, sequential mucus plugs from central to distal areas in the airway tree to be detected and included for analysis. Each bronchopulmonary segment will be given a score that directly represents the number of mucus plugs within that segment. Therefore, mucus plugs will be counted per segmental airway branch, and the total number of mucus plugs will be presented on a segmental, lobar (RUL, RML, RLL, LUL and LLL), and total level, by summing up the scores over the specific zones mentioned. The volume of the mucus plugs will also be determined on lobar (RUL, RUML, RLL, LUL and LLL) and presented on the total level, by summing up the mucus volumes over the specific zones mentioned.

Next, with the use of data presented from the mucus plugging assessment above, mucus plugs will also be scored with a scoring system similar to that by Dunican et al. with the Severe Asthma Research Program (SARP) (Dunican et al., 2018), based on bronchopulmonary segmental anatomy. Each bronchopulmonary segment will be given a score of 1 (mucus plug present) or 0 (mucus plug absent). The segment scores of each lobe will be summed to generate a total mucus score for both lungs, yielding a mucus score ranging from 0-20. Of note is the means of determining whether a particular segment contained a mucus plug will differ from that described in Dunican et al., 2018 in that airways will be segmented as described above. The presence or absence of mucus within a given CNN-segmented airway will be determined according to the method also described above.

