This is an interventional, single group, open-label, uncontrolled, prospective, multicenter clinical trial.

Disclosure Statement: This is a single group treatment study with one arm that has no masking.

Number of Participants:

Enrolled	Estimated 38 participants
Assigned	N/A (single-arm study)
Evaluable participants	Estimated 34 participants
Primary analysis population	Estimated 29 participants

Note: "Enrolled" means a participant's, or their legally acceptable representative's, agreement to participate in a clinical study following completion of the informed consent process. Potential participants who are screened for the purpose of determining eligibility for the study, but are not assigned in the study, are considered "screen failures", unless otherwise specified by the protocol.

Intervention Groups and Duration:

Each participant will be participating in the study for a minimum of 15 weeks (maximum of 23 weeks). Informed consent will be obtained from participants between 24 hours and 30 days prior to screening. Participants will be given instructions on how to adequately withhold their maintenance and rescue asthma medications prior to their screening visit. Once participants are enrolled into the study after screening, there will be a run-in period of 1 to 21 days (3 weeks) before Visit 1 (V1) at which time participants will undergo baseline assessments prior to receiving the first dose of benralizumab. There will be a total of three subcutaneously (SC) administered doses of benralizumab 30 mg given at weeks 0 (V1), 4 (V2), and 8 (V3). Final measurements will be taken at V4 at a minimum of 4 weeks to a maximum of 6 weeks after V3, followed by a 2-week follow-up period.

During the study, dose adjustment and dose interruption of benralizumab will not be permitted. Dosing can only be discontinued due to an AE per the Investigator's clinical judgement or unforeseen circumstances. Treatment rechallenge will not be permitted in this study and any participants who discontinue benralizumab will be considered a study withdrawal (see Section 7.1 for further details on criteria for discontinuation of study intervention).

Data Monitoring Committee: Not applicable

Statistical Methods:

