4.2 Scientific Rationale for Study Design

Single-arm design

The decision to conduct a single-arm study instead of a placebo-controlled study was based on several factors.

Firstly, benralizumab has been approved in all major markets, and its efficacy is established in the target patient population. While it is of scientific value to add a placebo arm to this study, this addition in the context of a phase IV study in a population prone to exacerbations, and

with the availability of other biologics for asthma, will complicate study enrolment and increase the number of patients enrolled on both arms, thus delaying the availability of important results from this study. Furthermore, having a placebo arm would be unnecessarily exposing patients to radiation through the study procedure.

Next, as previously discussed, it is noteworthy that FRI endpoints, unlike those derived from spirometry are not influenced by patient effort or muscle force, and are thus less likely to change due to a non-disease-related placebo effect. Several studies in asthma and COPD have demonstrated very low variability in FRI parameters when patients are not subjected to an intervention or when imaged after equivalent maintenance medication withhold periods (De Backer et al., 2012a; De Backer et al., 2016; De Backer et al., 2018; Langton et al., 2019).

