6.3 Measures to Minimize Bias: Randomization and Blinding

The current study is an open-label study with no blinding at site level.

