8.1 Efficacy Assessments

8.1.1 Functional Respiratory Imaging (FRI)

Functional Respiratory Imaging (FRI) is a quantitative method to measure biological responses to therapeutic interventions through structural and functional parameters using high-resolution CT and computational fluid dynamics. All CT scanners used in this study must be at least a 64-slice scanner. For a helical scan, the scanner should be able to acquire at least 64 slices per rotation using a slice thickness of 0.625 mm or lower (collimation of

64 x 0.625 mm, 128 x 0.5 mm, 256 x 0.6 mm, etc.) using a tube voltage of 100kV. FRI analyses will be conducted by a central vendor who will provide further guidance on the CT scanner requirements, CT scan procedure and scanner-specific scanning protocol settings required for the current study in a separate manual and guidance document. Study team training will also be provided by the central vendor to all relevant study team members prior to study center activation. Clinical evaluation of CT scans should be done by the study team as per local practice, and any abnormality identified should be recorded as an AE in the eCRF.

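### The plan does not require the central FRI analysts to be masked to visit, scan date or scan order, although the primary endpoint has a visual step and there is no control arm

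*Protocol*

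**What the plan says.** **Masking.** The synopsis states: "This is a single group treatment study with one arm that has no masking". Protocol 6.3, the section on measures against bias, consists of one sentence: "The current study is an open-label study with no blinding at site level".

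**Who reads the scans.** Protocol 8.1.1: "FRI analyses will be conducted by a central vendor". That section refers to separate vendor guidance, described as covering scanner requirements, the scan procedure and scanner settings. Reading is not in that description.

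**What happens before and during reading.** Protocol 8.1.1.1: "All high-resolution CT images should be de-identified before upload to the central vendor", and then "Trained FRI analysts will implement validated protocols and algorithms to convert the high-resolution CT images".

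**How mucus is assessed.** Protocol 8.1.1.2: "Mucus plugging will be assessed visually through diligent segmentation of the airways". It continues: "Airways will be segmented from central airways to distal airways by means of a deep learning Convolutional Neural Network (CNN) model". A plug is then defined by rule: it cuts the segmentation short, and open airway is present beyond it. Plug volumes are summed over lobes to give the total.

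**How the missing control arm is defended.** Protocol 4.2 gives several reasons. One is that FRI measures do not depend on patient effort and "are thus less likely to change due to a non-disease-related placebo effect".

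**What is not said.** The protocol, SAP and addendum do not state whether analysts see the visit or scan date, in what order the two scans are read, how far CNN output may be corrected by hand, or whether a second reader or an agreement check is used. The quality measures that are described (phantom scans, site certification, training of site staff) concern image acquisition.

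**The concern.** With one arm and one scanning session on each side of treatment, an analyst who could tell which scan came second would know treatment status exactly. The expected direction is written into the protocol: the synopsis and Section 2.1 both anticipate less mucus plugging after eosinophil depletion. A tendency to call fewer or smaller plugs on the later scan would pass straight into the mean change in mucus volume, the plug score and the lobe models. No control arm would subtract it.

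The patient-effort argument in 4.2 deals with bias arising from the patient. It does not deal with expectation in the person reading the scan. The 12-week placebo figure quoted there is for siVaw, so it does not show how stable mucus readings are. Section 4.2 calls the mucus volume method novel, and addendum 2.11 says the parameter has not been presented this way in earlier studies. Section 4.2 also treats a significant change in mucus volume as clinically meaningful, so a false positive would carry clinical weight. SAP 3.2.1.6 plans no sensitivity analysis of the primary endpoint.

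**Working it through.** **Step 1: does any statement on masking reach the analysts?**

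| Statement | What it covers | Does it settle visit masking of central analysts? |
|---|---|---|
| Synopsis, no masking | A single-group treatment study | No; image reading is not mentioned |
| 6.3, no blinding at site level | Sites | No; the vendor does the reading |
| 8.1.1.1, de-identification | Images before upload | No; the fields removed are not listed |
| 8.1.1, separate vendor guidance | Scanner, procedure, settings | No; reading is not among the topics named |

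The plan is therefore silent. It neither requires masked reading nor states that reading is unmasked.

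**Step 2: how much room is there for judgement?** Three features narrow it: CNN segmentation, the fixed occlusion rule, and validated protocols and algorithms. Two leave some open: the assessment is called visual, and no limit is placed on manual editing. The documents do not allow the remaining discretion to be measured.

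**Step 3: how sensitive is the primary test to a systematic reading shift?** This is an illustration, not an estimate of bias in this trial.

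Inputs: planned primary analysis population 29 and evaluable population 34 (synopsis); two-sided 5% level (Protocol 9.4.1); paired t-test (Protocol 9.4.2.1, SAP 3.2.1.4); null difference 0 (Protocol 9.1). The figure of 29 cannot be reproduced, because the effect size, SD and power are not in the visible text of 9.2. That is redaction, not a fault.

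Smallest observed mean change giving p < 0.05, in SDs of the paired differences:

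t(0.975, n − 1)/√n = t(0.975, 28)/√29 = 0.380; at n = 34 it is 0.349.

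Now set the true change to 0 and add a constant reading shift of d SD. The test statistic follows a noncentral t with n − 1 degrees of freedom and noncentrality d√n. The rejection probability is the sum of both tails beyond ±t(0.975, n − 1).

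| Assumed shift d | n = 29 | n = 34 |
|---|---|---|
| 0 | 5.0% | 5.0% |
| 0.1 | 8.2% | 8.7% |
| 0.2 | 18.0% | 20.5% |
| 0.3 | 34.5% | 39.7% |

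The calculation takes normal differences, a shift that is the same for everyone, and an unchanged SD. Addendum 2.11.3 allows a log-plus-one transformation, so d is in SDs of whatever scale is analysed and has no fixed meaning in volume.

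**Step 4: would masked reading conflict with the planned measurements?** No. The primary parameter is untrimmed. Trimmed parameters need to know which two scans belong together (Protocol 8.1.1.1), but not which came first.

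**The case against.** A reader might infer that the analysts are in fact unmasked to visit. The documents do not support that. The synopsis statement describes the treatment design, Section 6.3 is limited to sites, and the vendor's reading procedures are not among the documents. The vendor may already mask.

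A reader might also infer that de-identification hides the patient but leaves the visit visible. The protocol does not say which fields are removed, so neither conclusion can be drawn.

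A third tempting reading is that the endpoint is essentially a subjective visual score. That gives too little weight to the CNN, the fixed plug definition and the validated protocols.

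The case for the single-arm design in 4.2 is also wider than patient effort. It cites established efficacy, radiation exposure, enrolment burden and repeat-scan stability. Finally, the shifts in the table are assumed, and the same table would apply to any paired t-test at these sample sizes.

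All of this stands, and it limits the point to what the plan requires. It does not remove the point. As written, the plan would permit unmasked reading of an uncontrolled primary endpoint whose expected direction is stated. If masking is already vendor practice, a sentence recording it closes the gap.

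**Conclusion.** The point holds as a cheap improvement: masking of the central analysts to visit, date and order is not required anywhere in the protocol, SAP or addendum, in a design with no other protection against a systematic reading shift. It is not a finding that the readings are biased. Whether any reader bias exists, and how large it is, cannot be known from these documents. The error rates of about 8%, 18% and 34.5% at n = 29 depend entirely on the assumed shifts of 0.1, 0.2 and 0.3 SD and show only that a modest shift would matter at this sample size.

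**What to change.** In Protocol 6.3 and 8.1.1.2, require that:

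- visit and scan date are removed from file names and image headers before reading;
- each participant's two TLC scans are labelled A and B in random order;
- plug calls and volumes are locked before the code is released.

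The same text should say how far analysts may edit the CNN output. Pairing for the trimmed secondary parameters can stay.

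The cost is a relabelling step at the vendor and a wait until both scans are in. No extra analysts or scans are needed.

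Addendum 2.14 mentions a dry run that already held FRI data, so some scans may have been read. In that case the CSR should report how they were read, masked or not. If they were read unmasked, it should state this as a limitation of the primary result. A masked re-read of the TLC mucus data is optional.
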